12.2.2 Safety and Tolerability

Safety and tolerability of tipifarnib will be assessed based on the following:

- Incidence, duration, and severity of TEAEs, SAEs, AEs resulting in permanent discontinuation of study drug, and deaths within approximately 30 days from the last dose of study drug (or immediately before the administration of another anticancer treatment)
- Changes in laboratory test results

AEs will be coded using the latest available version of the Medical Dictionary for Regulatory Activities (MedDRA). TEAEs are defined as AEs that start on or after the first dose of study

drug and within approximately 30 days of the last administration of study drug. AEs will be summarized by the number and percentage of subjects who experienced the event, according to system organ class and preferred term. A subject reporting multiple cases of the same AE will be counted once within each system organ class and similarly counted once within each preferred term

Unless specified otherwise, the denominator for these calculations will be based on the number of subjects in each cohort who received at least one administration of tipifarnib, irrespective of the total number of doses or treatment cycles administered. These conventions will be appropriately modified to calculate AE incidence rates separately for each cycle that study therapy is administered. AE incidence rates may also be calculated based on other measures of subject exposure (e.g., total number of treatment cycles administered). AEs will also be summarized by NCI CTCAE v.4.03 severity grade, by relationship to each study drug and by treatment regimen. Additional summaries may also be provided for SAEs, and events resulting in the permanent discontinuation of therapy. All AEs will be included in individual subject listings.

The incidence of grade 3 and 4 hematological toxicities (including neutropenia, thrombocytopenia, and anemia) will be provided by treatment cycle and across all treatment cycles. The toxicity grades for laboratory tests will be based on NCI CTCAE v.4.03 criteria. The use of blood transfusions (platelets, red blood cells, whole blood) and/or growth factor support will be reported.

Vital sign results (heart rate, blood pressure and temperature) will be summarized descriptively for each scheduled and unscheduled protocol time point. Changes will be calculated relative to the assessments at baseline.

Sample Size Determination

A two-stage study design was selected in order to minimize the number of study subjects treated if tipifarnib were considered not sufficiently efficacious to grant further development in this subject population. This design is intended to allow the termination of accrual in case of unacceptably low efficacy as measured by ORR and will be evaluated in a FAS basis.

In the first stage, 22 eligible subjects will be enrolled and randomized in to one of two dose regimen cohorts (11 subjects per cohort). If two or more responses are observed in a given dose regimen cohort, 7 additional study subjects will be enrolled. Each dose regimen cohort is designed to test the null hypothesis of ORR rate less than 10% vs alternative hypothesis of ORR rate at least 30% and will be evaluated independently. At the completion of the study, treatment will be considered of further interest if 4 or more subjects in the 18 subject dose regimen cohort achieve a response, i.e. the true ORR is higher than 10%.

To determine the total trial size, a response of interest of 30% is assumed. This design provides 80% power to detect a difference between 10% and 30% RBC TI rate at one-sided significance level of 0.087. Using this design, the probability of terminating each stratum at the end of stage 1 if the true rate is 10% is 0.697 while the probability of terminating each stratum at the end of stage 1 if the true rate is 30% is 0.113.

The performance characteristics of this approach are shown in Table 7.

Table 6: Performance characteristics for sample size determination

	Probability to conclude TRUE rate > 0.10 if TRUE underlying RBC TI response rate is as indicated		
TRUE Rate>	0.1	0.3	0.4
N=11	0.09	0.69	0.88
N=18	0.1	0.83	0.97
N=25	0.1	0.91	0.99
N=32	0.09	0.95	>0.99

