Each dose regimen cohort is designed to test the null hypothesis of ORR less than 10% vs alternative hypothesis of ORR rate at least 30%. At the completion of the study, treatment will be considered of further interest if 4 or more subjects in the 18 subject dose regimen cohort achieve a response, i.e. the true ORR rate is higher than 10%.

To determine the total trial size, a response of interest of 30% is assumed. This design provides 80% power to detect a difference between 10% and 30% ORR at one-sided significance level of 0.087 at each dose cohort. Using this design, the probability of terminating a cohort at the end of stage 1 if the true rate is 10% is 0.697 while the probability of terminating the cohort at the end of stage 1 if the true rate is 30% is 0.113.

STUDY ASSESSMENTS:

Table 1: Schedule of Activities

	Screening ¹	Cycle (28 days)		End of	Follow	Follow
Activity		Day 1 (±2d)	Day 22 (± 5d) ²	Treatment Visit ³	Up Visit ⁴	Up Contact ⁵
ICF, Inclusion/exclusion criteria evaluation, HIPAA form	X			•		
Medical History ⁶	X					
Record the number of RBC, whole blood and platelet transfusions ⁷	X	X	X	X	X ²⁴	
Concomitant medications ⁸	X (assessed at each study visit and as clinically needed)					
AE assessment ⁸	X (asses	sed at each st	udy visit and a	s clinically need	led)	
ECOG performance status	X ⁹	X		X		
Height	X					
Weight	X ⁹	X ¹⁰		X		
Vital signs (heart rate, blood pressure, temperature)	X ⁹	X ¹⁰		х		
Complete physical examination	X ⁹			X		
Symptom based physical examination		X	X			
Pregnancy test ¹²	X ¹¹	X^{13}		X		
Serum chemistry ¹⁴	X	X^{16}		X		
Hematology ¹⁴	X ¹⁵	X ¹⁵	X	X	X^{17}	
Coagulation ¹⁴	X			X		
Disease Response Assessment ¹⁸			X	X	X ²⁴	
Perform bone marrow aspirate ^{19, 20}	X ²¹		X ²²	X ²³	X ^{23, 24}	
Tipifarnib administration ³⁰		X	X ³²			
Drug accountability ³¹		X^{13}		X		
Collection of survival and anticancer treatment information						X

- Screening evaluations will be completed within 4 weeks (28 days) of Cycle 1 Day 1. Evaluations performed as part of the standard of care within 28 days of dosing but prior to consent do not need to be repeated. By signing the consent form, study subjects agree to the collection of standard of care health information.
- 2. Day 22 visit (± 5 days) should be performed during cycles 3, 6, 9 and 12, and every 3rd cycle thereafter.
- An End of Treatment visit will be conducted within 30 days (± 7 days) from the last dose of tipifarnib or immediately before

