8 TRIAL DESIGN

8.1 Study Design

This phase 2 study will investigate the antitumor activity in terms of ORR of tipifarnib in approximately 36 eligible subjects with MDS who have no known curative treatment.

A two-stage study design was selected in order to minimize the number of study subjects treated if tipifarnib were considered not sufficiently efficacious to grant further development in this subject population. This design is intended to allow the termination of accrual in case of unacceptably low efficacy as measured by ORR.

In the first stage, 22 eligible subjects will be enrolled and randomized in to one of two dose regimen cohorts (11 subjects per cohort). If two or more responses are observed in a given dose regimen cohort, 7 additional study subjects will be enrolled. Each dose regimen cohort is designed to test the null hypothesis of ORR rate less than 10% vs alternative hypothesis of ORR rate at least 30% and will be evaluated independently. At the completion of the study, treatment will be considered of further interest if the true ORR rate is higher than 10% (at least 4

responders out of 18 subjects in a dose regimen cohort). This design provides 80% power to detect a difference between 10% and 30% ORR rate at one-sided significance level of 0.087.

Only consented subjects who meet all eligibility criteria will be enrolled in the study. Screening evaluations will be completed within 4 weeks (28 days) of Cycle 1 Day 1. Any screening evaluation, including disease status, will need to be repeated if performed more than 4 weeks from Cycle 1 Day 1. Evaluations performed as part of the standard of care within 28 days of dosing but prior to consent, do not need to be repeated. By signing the consent form, study subjects agree to the collection of standard of care health information.

Subjects will be randomized to receive tipifarnib orally with food, twice a day (bid) according to one of the following dose regimens:

• Regimen 1: 600 mg bid for 7 days on Days 1-7 in 28 day cycles (i.e. 1 week on / 3 weeks off).

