10.1 Efficacy Variables

Hematologic assessments, including peripheral blood evaluations and review of transfusion requirements, will be performed at screening and at least monthly until disease progression. Disease assessments will also be performed at screening and at least once every approximately 12 weeks starting at the end of cycle 3. As part of the disease assessment at screening and during Cycles 3, 6 and 9, bone marrow evaluation will be performed. Thereafter, bone marrow evaluations will occur during disease assessments in accordance with institutional standard practice. Additional hematologic or disease assessments may be conducted if deemed necessary by the Investigator.

Disease response assessment will be performed by the Investigator according to the MDS IWG criteria (Table 9 and Table 10).

Determination of RBC TI (secondary endpoint) will be assessed by the investigator through the review of subject transfusion requirements and hemoglobin levels. RBC TI will be defined as the absence of the intravenous infusion of any RBC transfusion during any consecutive "rolling" 56 days during the treatment period, i.e. days 1 to 56, days 2 to 57, days 3 to 58, etc. and $a \ge 1$ g/dL increase in hemoglobin level.

Upon disease progression, all subjects in the study cohort will be followed approximately every 12 weeks for survival and the use of subsequent therapy until either death or 12 months after accrual of the study cohort has been completed, whichever occurs first. Information on survival and subsequent anticancer therapy may be collected by phone.

Subjects who terminate treatment for reasons other than death or disease progression will be assessed at regular intervals for disease progression (approximately every 12 weeks) and leukemic transformation (monthly blood counts). Disease assessments performed during the first 9 months from the start of the subject's participation in the study will include bone marrow evaluation. Thereafter, bone marrow evaluations will occur during disease assessments in accordance with institutional standard practice. These assessments will continue until disease progression, withdrawal of subject's consent to study procedures or initiation of another anticancer therapy.

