5. SAMPLE SIZE DETERMINATION

A two-stage study design was selected in order to minimize the number of study subjects treated if tipifarnib were considered not sufficiently efficacious to grant further development in this subject population. This design is intended to allow the termination of accrual in case of unacceptably low efficacy as measured by ORR and will be evaluated in a FAS basis.

In the first stage, 22 eligible subjects will be enrolled and randomized in to one of two dose regimen cohorts (11 subjects per cohort). If two or more responses are observed in a given dose regimen cohort, 7 additional study subjects will be enrolled. Each dose regimen cohort is designed to test the null hypothesis of ORR rate less than 10% vs alternative hypothesis of ORR rate at least 30% and will be evaluated independently. At the completion of the study, treatment will be considered of further interest if 4 or more subjects in the 18 subject dose regimen cohort achieve a response, i.e. the true ORR is higher than 10%.

To determine the total trial size, a response of interest of 30% is assumed. This design provides 80% power to detect a difference between 10% and 30% red blood cell (RBC) transfusion independence (TI) rate at one-sided significance level of 0.087. Using this design, the probability of terminating each stratum at the end of stage 1 if the true rate is 10% is 0.697 while the probability of terminating each stratum at the end of stage 1 if the true rate is 30% is 0.113.

The performance characteristics of this approach are shown in Table 3.

Table 2: Performance characteristics for sample size determination

		Probability to conclude TRUE rate > 0.10 if TRUE underlying RBC TI response rate is as indicated		
TRUE Rate -->		0.1	0.3	0.4
TRUE Rate -->	N=11	0.09	0.69	0.88
TRUE Rate -->	N=18	0.1	0.83	0.97
TRUE Rate -->	N=25	0.1	0.91	0.99
TRUE Rate -->	N=32	0.09	0.95	>0.99

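### The performance table in protocol 12.4 and SAP 5 gives single-stage probabilities for a two-stage design, and the power statement names RBC transfusion independence instead of ORR

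*Protocol*

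**What the plan says.** Protocol section 12.4 (Sample Size Determination) and SAP section 5 describe the same design for each dose regimen cohort. Eleven subjects are treated first. Two or more responses bring in 7 more, and 4 or more responses among 18 count as success. The null ORR is 10% and the ORR of interest is 30%.

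The operating characteristics in the text are 80% power, one-sided alpha 0.087, and Stage 1 stopping probabilities of 0.697 at a true rate of 10% and 0.113 at 30%. The protocol puts the last of these as "the probability of terminating each stratum at the end of stage 1 if the true rate is 30% is 0.113".

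A table follows, introduced by "The performance characteristics of this approach are shown in Table 7" and headed "Probability to conclude TRUE rate > 0.10 if TRUE underlying RBC TI response rate is as indicated". It has rows for N = 11, 18, 25 and 32. The N=18 row reads 0.1 / 0.83 / 0.97 at true rates of 10% / 30% / 40%. The SAP copy has the same header and cells.

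The endpoint in the power sentence differs between sections:

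- Protocol 12.4: "This design provides 80% power to detect a difference between 10% and 30% RBC TI rate at one-sided significance level of 0.087".
- SAP 5: "difference between 10% and 30% red blood cell (RBC) transfusion independence (TI) rate at one-sided significance level of 0.087".
- Protocol 8.1: "This design provides 80% power to detect a difference between 10% and 30% ORR rate at one-sided significance level of 0.087". The synopsis also says ORR.
- Protocol 10.1, on the status of transfusion independence: "Determination of RBC TI (secondary endpoint) will be assessed by the investigator".

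**The concern.** There are two faults in one place.

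First, the text and the table give different figures for the same 18-subject cohort: 80% against 83% power at a true rate of 30%, and 0.087 against 0.1 at 10%. Nothing says that the table ignores the Stage 1 stop. A reader who relies on the table takes the chance of missing a 30% ORR to be 17% (1 − 0.83), when under the stated rule it is 20% (1 − 0.80).

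Second, the sample-size section is the formal record of what the trial is powered for, and in both documents it attaches the power to a secondary endpoint. ORR and RBC transfusion independence are defined differently (protocol 12.2.1), so the label is not a synonym. SAP section 15 reports no changes from the protocol, so nothing there corrects it. Anyone drafting the study report from these sections would carry both errors forward.

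**Working it through.** **Inputs** (protocol 12.4, repeated in SAP 5): Stage 1 n = 11; continue if X1 ≥ 2; Stage 2 adds 7; success if X1 + X2 ≥ 4 of 18. The true rates p in the table are 0.10, 0.30 and 0.40.

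**Formulas** (exact binomial, X1 ~ Bin(11, p), X2 ~ Bin(7, p)):

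- Early stop: P(X1 ≤ 1)
- Success: P(X1 = 2)·P(X2 ≥ 2) + P(X1 = 3)·P(X2 ≥ 1) + P(X1 ≥ 4)

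**Step 1: reproduce the figures in the text.**

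- At 30%, early stop = 0.0198 + 0.0932 = 0.113. Success = 0.1998 × 0.6706 + 0.2568 × 0.9176 + 0.4304 = 0.1339 + 0.2357 + 0.4304 = 0.800.
- At 10%, early stop = 0.3138 + 0.3835 = 0.697. Success = 0.2131 × 0.1497 + 0.0710 × 0.5217 + 0.0185 = 0.0319 + 0.0371 + 0.0185 = 0.0875 (0.08749 unrounded, hence 0.087).
- At 40%, early stop = 0.030 and success = 0.951.

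The text's 80%, 0.087, 0.697 and 0.113 are all correct for the stated rule.

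**Step 2: find what the table shows.** Single-look tails P(X ≥ r | N), with r chosen to match the printed row:

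| Row | Rule | 10% | 30% | 40% | Printed |
|---|---|---|---|---|---|
| N=11 | ≥3 | 0.0896 | 0.6873 | 0.8811 | 0.09 / 0.69 / 0.88 |
| N=18 | ≥4 | 0.0982 | 0.8354 | 0.9672 | 0.1 / 0.83 / 0.97 |
| N=25 | ≥5 | 0.0980 | 0.9095 | 0.9905 | 0.1 / 0.91 / 0.99 |
| N=32 | ≥6 | 0.0944 | 0.9490 | 0.9972 | 0.09 / 0.95 / >0.99 |
| Stated two-stage rule | ≥2/11, then ≥4/18 | 0.0875 | 0.8001 | 0.9507 | not in the table |

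Eleven of the 12 cells agree by ordinary rounding. The exception is 0.8354, which appears as 0.83 and so would have to have been truncated.

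**Step 3: account for the gap.** Single look minus two-stage should equal the chance of stopping at Stage 1 when all 18 subjects would have given at least 4 responses: P(X1 = 0)·P(X2 ≥ 4) + P(X1 = 1)·P(X2 ≥ 3).

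- At 30%: 0.0198 × 0.1260 + 0.0932 × 0.3529 = 0.0025 + 0.0329 = 0.0354, and 0.8354 − 0.8001 is the same to rounding.
- At 40%: 0.9672 − 0.9507 = 0.0165.
- At 10%: 0.0982 − 0.0875 = 0.0107.

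The Stage 1 stop explains the whole difference.

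**Step 4: check within the section itself.** With a 0.113 chance of stopping at 30%, no final rule behind this Stage 1 gate can succeed more often than 1 − 0.113 = 0.887. At 40% the limit is 1 − 0.030 = 0.970. The N=25 and N=32 rows print 0.91 and 0.95 at 30%, and 0.99 and >0.99 at 40%. They cannot describe a design with this gate.

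**Step 5: endpoint.** In protocol 12.4 and SAP 5, the futility purpose, the null, the alternative and the 4-of-18 rule are all stated for ORR. Only the power sentence and the table header say RBC TI. The primary objective, the synopsis and protocol 8.1 say ORR.

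**The case against.** Several points can be made for the plan.

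- *The table may compare fixed sample sizes.* Its caption refers to sample size determination, and 25 and 32 are not cohort sizes here, so those rows need not share the Stage 1 gate. The limit in Step 4 binds only if they do. That is a fair reading of how the table arose. But the sentence above the table presents it as the performance of the two-stage approach, and no row is labelled otherwise.
- *Another rule fits the N=18 row.* Stopping only on 0 of 11 gives 0.097 / 0.833 / 0.966, which rounds exactly to the printed cells. It is not the stated rule. Applied to the other rows it gives 0.901 at N=25 and 0.936 at N=32 against 0.91 and 0.95 printed, so single-look tails remain the better explanation. On either account the row is not the stated design. The cut-offs of 3, 5 and 6 are inferred, and the sponsor should confirm them.
- *The alpha discrepancy is soft.* 0.087 also rounds to 0.1 at one decimal. This stands as a caution, although other cells in that column show 0.09.
- *The consequence is small.* The correct figures sit just above the table, no analysis uses it, and context makes clear that the decision rests on ORR. All true, and it limits the weight of the point. It does not remove two different powers and a wrong endpoint from the formal sample-size section of both documents.

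**Conclusion.** The point holds. Under the stated rule the N=18 row should read 0.087 / 0.80 / 0.95. The printed row overstates power by about 3 points at 30% and 2 points at 40%, and apparently overstates alpha by about 1 point. The RBC TI label is wrong in the power sentence and the table header of both documents.

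The two-stage values rest only on the stated rule and exact binomial probabilities for independent subjects. That the table came from single-look calculations is an inference from the match across all four rows. The mismatch with the stated design does not depend on it. The 80% power, 0.087 alpha, stopping probabilities, sample size and both decision rules are sound and stay as they are. This is a correction that should be made, but not a flaw in the design.

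**What to change.** In protocol Table 6 and the SAP section 5 table:

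1. Replace the N=18 row with the two-stage values 0.087 / 0.80 / 0.95.
2. Delete the N=11, 25 and 32 rows, or label them as single-stage with their cut-offs (≥3, ≥5, ≥6) once the sponsor confirms these.
3. Change RBC TI to ORR in the power sentence and the table header.
4. Align the table numbers. The protocol text cites Table 7 but the caption says Table 6. The SAP text and list of tables say Table 3 but the caption says Table 2.

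A minor wording change could go into the same edit. The documents gloss 4 of 18 as showing that the true rate exceeds 10% (synopsis: "achieve a response, i.e. the true ORR rate is higher than 10" per cent). It would be more exact to say that the null ORR of 10% is rejected at one-sided 0.087. The planned two-sided 95% exact interval is stricter and includes 10% at 4/18 (6.4% to 47.6%) and at 5/18 (9.7% to 53.5%), so the present wording could appear to conflict with the reported interval.

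The cost is table and label corrections in two documents, with no change to design or analysis. The tabulated power becomes slightly less favourable.

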12.5 Changes in the Conduct of the Study or Planned Analyses

Only the Sponsor, upon consultation with the principal Investigator may modify the protocol. The Sponsor will issue a formal protocol amendment to implement any changes. The only exception is when an Investigator considers that a subject's safety is compromised without immediate action. In these circumstances, immediate approval of the chairman of the IRB/IEC must be sought, and the Investigator should inform the Sponsor and the full IRB/IEC within 2 working days after the emergency has occurred.

The IRB/IEC must review and approve all protocol amendments. Protocol amendments that have an impact on subject risk or the study objectives, or require revision of the ICF, must receive approval from the IRB/IEC prior to their implementation.

When a protocol amendment substantially alters the study design or the potential risks or burden to subjects, the ICF will be amended and approved by the Sponsor and the IRB/IEC, and all active subjects must again provide informed consent.

13 ETHICAL AND REGULATORY ASPECTS

13.1 Responsibilities of the Investigator

The Investigator is responsible for the conduct of the study at his/her site. He/she will ensure that the study is performed in accordance with the clinical study protocol and with the ethical principles that have their origin in the Declaration of Helsinki, as well as with the ICH Note for Guidance on Good Clinical Practice (ICH Topic E6, 1996) and applicable regulatory requirements. In particular, the Investigator must ensure that only subjects who have given their informed consent are included into the study.

13.2 Subject Information and Informed Consent

An unconditional prerequisite for a subject's participation in the study is his/her written informed consent. The subject's written informed consent to participate in the study must be given before any trial-related activities are carried out.

Adequate information must therefore be given to the subject by the Investigator before informed consent is obtained (a person designated by the Investigator may give the information, if permitted by local regulations).

With the cooperation of the Sponsor, and in accordance with the Note for Guidance on Good Clinical Practice (ICH Topic E6, 1996), and the ethical principles that have their origin in the Declaration of Helsinki, the Investigator will prepare the informed consent form and other written information to be used in obtaining informed consent from the study subjects. The Investigator should cooperate with the sponsor for preparation of aforementioned written information.

Before the consent may be obtained, the potential subject (or the potential subject' legally acceptable representative) should be provided with sufficient time and opportunity to be accessed to the details of clinical study and to decide if they would participate in the study. All the queries related to the study from the potential subject or legally acceptable representative should be answered by the Investigator or collaborators.

In addition to providing this written information to a potential subject, the Investigator or his/her designee will inform the subject verbally of all pertinent aspects of the study. The language used in doing so must be chosen so that the information can be fully and readily understood by lay persons.

Depending on local regulations, a person other than the Investigator may inform the subject and sign the ICF. Where the information is provided by the Investigator, the ICF must be signed and personally dated by the subject and the Investigator. The signed and dated declaration of informed consent will remain at the Investigator's site, and must be safely archived by the Investigator so that the forms can be retrieved at any time for monitoring, auditing and inspection

purposes. A copy of the signed and dated information and ICF should be provided to the subject prior to participation.

Whenever important new information becomes available that may be relevant to the subject's consent, the written subject information sheet and any other written information provided to subjects will be revised by the Sponsor and be submitted again to the IRB/IEC for review and favorable opinion. The agreed, revised information will be provided to each subject in the study for signing and dating. The Investigator will explain the changes to the previous version.

